3.4.5. Pharmacokinetic (PK) Population

The Pharmacokinetic (PK) Population includes all subjects in the Safety Population receiving active study treatment and having at least one measurable plasma concentration of study treatment at any timepoint.

3.4.6. Intensive Pharmacokinetic (IPK) Subset Population

The Intensive PK Subset Population includes subjects in the PK population participating in the intensive PK sampling.

3.4.7. Safety Long-Term Follow-Up (SAF LTFU) Population

The Safety Long-Term Follow-Up Population includes all subjects in the Randomized Population who receive at least one dose of the study treatment and consented to be a part of the long-term follow-up. Subjects will be analyzed in the treatment group that corresponds to the study treatment received during the study.

3.4.8. Intent-to-Treat-c Long-Term Follow-Up (ITT-c LTFU) Population

The Intent-to-Treat Long-Term Follow-Up Population includes all subjects in the SAF LTFU who have met the ITT-c criteria and have any Week 12 or Week 24 assessment completed.

4. Subject Disposition

4.1. Disposition

A subject will be considered to have completed the study after his/her attendance at the last planned study visit (Day 33 ± 1 day), or the last unscheduled visit (if any occur), as applicable. For each subject his or her study completion status (Yes/No) is recorded on the End of Study CRF.

The number of subjects randomized and in the SAF, ITT-c, PP, PK and IPK populations will be summarized using frequencies and percentages. All percentages will be based on the number of subjects randomized.

Subject disposition will be summarized by treatment group and overall, for all subjects who are randomized. A disposition of subjects includes the number and percentage of subjects for the following categories: subjects who were randomized, subjects who completed study treatment per protocol, subjects who discontinued study treatment early, subjects who completed the study, subjects who discontinued from the study early. All percentages will be based on the number of subjects randomized. The reasons for discontinuation of study treatment and study participation will also be summarized in this table.

The reason for discontinuation of study treatment or study participation may include any of the following:

- Adverse event
- Lost to follow-up
- Pregnancy
- Protocol deviation
- Study terminated by sponsor
- Withdrawal by subject
- Physician decision
- Death
- Other reason

Subject disposition data will also be presented in listings, including a listing by analysis population.

Screen failures were not included in the study database and will not be included in any SDTM or ADaM datasets. If required, a listing of screen failures from all screened subjects, including the inclusion or exclusion criteria that were not met, may be provided from vendor IRT data.

A separate listing of subjects that were randomized, treated and then found to meet exclusion or fail to meet inclusion criteria will be provided including the inclusion or exclusion criteria.

4.2. Protocol Deviations

All protocol deviations (both significant and non-significant) will be entered and tracked in [REDACTED] Clinical Trial Management System (CTMS) by the study team throughout the conduct of the study in accordance with [REDACTED] Study Deviation Rules Document. A significant deviation is any deviation that may affect primary efficacy analyses, safety assessments, the safety or mental integrity of a subject, or the scientific value of the trial.

Data will be reviewed by the study team prior to unblinding and closure of the database to ensure all significant deviations and those leading to exclusion from analysis are captured and properly categorized. Particularly, deviations leading to exclusion from the PP population will also be determined by the study team and flagged in the final CTMS Deviation Data file.

Significant protocol deviations will be summarized by treatment group and overall. Separate listings will be provided for significant and non-significant protocol deviations. Summaries will be conducted on the randomized population.

5. Demographics and Baseline Characteristics

5.1. Demographics and Baseline Clinical Characteristics

A summary of demographics and baseline information will be presented by treatment group and overall, for all subjects in the SAF, ITT-c and PP populations.

For the SAF LTFU and ITT-c LTFU, a summary will be presented by treatment group and separately for reinfection status at Week 12 and Week 24 [positive, negative, and overall (including missing)] [Section 8.3.21](#) and [8.3.21](#).

Demographics and baseline clinical characteristics include:

- Age
- Sex
- Race (if available)
- Ethnicity (if available)
- Childbearing potential (for female subjects only)
- Post-menopausal (for female subjects only)
- Duration of COVID-19 symptoms
- Cigarette Smoking history
- COVID-19 vaccine history
- Weight (kilograms)
- Height (centimeters)
- Body mass index (calculated as (body weight in kilograms) / (height in centimeters / 100)²).

Subject demographic and baseline clinical characteristics will also be presented in a listing for all subjects in the SAF, ITT-c and PP population.

5.2. Medical History

Medical history will be coded using the Medical Dictionary for Regulatory Activities (MedDRA) Version 25.0 or higher. The number and percentage of subjects with any relevant medical history will be summarized overall and for each system organ class and preferred term. Percentages will be calculated based on number of subjects in the SAF population.

Subject medical history data including specific details, will also be presented in a listing.

5.3. Baseline Disease Characteristics

The following baseline disease characteristics will be presented by treatment group and overall and stratified by age group and duration of baseline COVID-19 symptoms (≤ 3 days or > 3 days and ≤ 5 days) for all subjects in the SAF, ITT-c and PP populations. Additionally, baseline disease characteristics will be listed for all subjects in the SAF population.

- SARS-CoV-2 RNA viral load
- Infectious SARS-CoV-2 viral load
- SARS-CoV-2 RNAemia
- SARS-CoV-2 serostatus
- Respiratory pathogen test
- SARS-CoV-2 variant
- COVID-19 symptom diary total score

- COVID-19 symptom diary severity

SARS-CoV-2 RNA viral load, Infectious SARS-CoV-2 viral load and SARS-CoV-2 RNAemia will also be summarized as positive, negative and missing where either a numeric or “POS” result is considered positive and TND is considered negative.

Baseline SARS-CoV-2 serostatus will be based on Day 1 SARS-CoV-2 anti-nucleocapsid and anti-spike IgG, and IgM antibodies. If at least one qualitative result is positive or IgM > 1.0, the serostatus will be considered positive. In order to be considered negative, all four results must be non-missing, all qualitative results must be negative and IgM equal to “<1.0”.

A description of how symptoms are scored from the COVID-19 Symptom Diary is in [Appendix 14.2](#). The total symptom score and the following severity categories will be presented:

- Only mild symptoms at Day 1
- 1 moderate and no severe symptoms
- 2 or more moderate symptoms and no severe symptoms
- 1 or more severe symptom(s) and no moderate symptoms
- 1 or more severe symptom(s) and 1 or more moderate symptom(s)

6. Treatments and Medications

6.1. Prior and Concomitant Medications

Any medication or therapy taken within one month of signing the ICF and during the study throughout the end of the study will be collected on the CRF. All medications will be coded using the World Health Organization Anatomical Therapeutic Chemical (ATC) Level 2 Classification and World Health Organization preferred term from the WHO Global Drug Dictionary version September 2022 B3 or later.

Prior medications are defined as those medications with a start date prior to the date of first dose of study treatment. Concomitant medications are defined as any medications with a start date on or after the date of first dose of study treatment or any medications with a start date prior to the date of first dose and a stop date after the date of first dose. Furthermore, a medication could be labeled as both a prior and concomitant medication if it was started prior to the first dose of study treatment and continued after the first dose of study treatment.

The number and percentages of subjects with at least one prior medication will be summarized by treatment group and overall. The number and percentages of all prior medications will be summarized by treatment group and overall and listed by Anatomical Therapeutic Chemical (ATC) level 2 and preferred term. All summaries will be performed using the SAF population.

The number and percentages of subjects with at least one concomitant medication will be summarized by treatment group and overall. The number and percentages of all concomitant medications will be summarized by treatment group and overall and listed by Anatomical Therapeutic Chemical (ATC) level 2 and preferred term. All summaries will be performed using

the SAF population. Additionally, prior and concomitant medications will be summarized for the long-term follow-up period using the Safety Long-Term Follow-Up population.

Prior and concomitant medications, including prohibited medication, will also be presented in a listing. Details for imputing missing or partial start and/or stop dates of medications are described in [Appendix 14.5](#).

6.2. COVID-19 Vaccination History

COVID-19 vaccination history includes whether a subject has been vaccinated, the type of vaccination, and the date and dose of the vaccination. COVID-19 vaccination history will be summarized overall and by treatment group in a table and presented in a listing.

6.3. Prior and Concomitant Therapies

Prior and concomitant therapies include surgical interventions, procedures, COVID-19 related oxygen supplementation, or other non-medication treatments. All reported therapies will be coded using the Medical Dictionary for Regulatory Activities (MedDRA) Version 25.0 or higher and classified by system organ class (SOC) and preferred term (PT).

Prior therapies are defined as those therapies with a start date prior to the date of first dose of study treatment. Concomitant therapies are defined as any therapies with a start date on or after the date of first dose of study treatment or any therapies with a start date prior to the date of first dose and a stop date after the date of first dose. Furthermore, a therapy could be labeled as both a prior and concomitant therapy if it was started prior to the first dose of study treatment and continued after the first dose of study treatment.

Concomitant therapies will be summarized by treatment group and overall based on the reported categories, as applicable, and by SOC and PT. Both prior and concomitant therapies will be presented in one listing. Additionally, prior and concomitant therapies will be summarized for the long-term follow-up period using the Safety Long-Term Follow-Up population. Additional details for supplemental oxygen use will be presented in a separate listing. Details for imputing missing or partial start and/or stop dates of medications are described in [Appendix 14.5](#).

6.4. Study Treatments

6.4.1. Extent of Treatment Exposure and Compliance

Duration of study treatment in days will be calculated as: last dose date – first dose date + 1 day, regardless of study treatment interruption (i.e., missed dose). Study treatment exposure (total study treatment administered in mg) will be summarized by treatment group and overall using the safety population.

The study treatment compliance will be calculated as: $100 * (\text{total number of days compliant} / \text{number of days of treatment planned per protocol})$, where a day of compliance is defined as taking one capsule per bottle on consecutive days for Days 1 to 5.

Study treatment compliance will be summarized for all subjects in the SAF population with descriptive statistics by treatment group and overall. Additionally, the number and percentages of subjects who completed treatment per protocol and in each compliance category (<80%, ≥80% to ≤100%) will be also presented by treatment group and overall.

A summary of each subject's exposure and compliance will also be presented in a listing.

7. Safety Analysis

The primary objective of the study is to evaluate the safety and tolerability of EDP 235 compared to placebo as assessed by, but not limited to, adverse events, clinical laboratory results, and vital signs. All safety analyses will be conducted on the safety population. Safety data, including treatment emergent adverse events (TEAEs), serious adverse events (SAEs), vital sign measurements, and laboratory values, will be summarized separately by treatment group.

7.1. Adverse Events

Adverse events will be summarized by the MedDRA version 25.0 or higher using SOC and PT by treatment group and all summary table percentages will be calculated out of the number of subjects in the Safety population. All events of SARS-CoV-2 reinfection will be considered adverse events. Additionally, adverse events will be summarized for the long-term follow-up period using the Safety Long-Term Follow-Up population and will not include any treatment discontinuation summaries.

All AEs will be presented in a data listing.

7.1.1. Treatment-Emergent Adverse Events

AEs that occur or worsen on or after the date and time of first dose of study treatment through Day 33 are considered Treatment-Emergent Adverse Events (TEAEs) and will be used for safety analyses.

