2.1. Overall Study Design and Plan

This is a randomized, double-blind, placebo-controlled, parallel group, multi-site study in non-hospitalized adult subjects who test positive for SARS-CoV-2 and have COVID-19 symptom onset within 5 days of randomization and who are not at high risk for progression to severe COVID-19. Subjects can be vaccinated or unvaccinated for COVID-19. Subjects with prior COVID-19 infection <90 days before enrollment and/or who received a COVID-19 vaccine dose <90 days before enrollment are excluded from trial participation.

[figure not shown]
Subjects will be randomized in a 1:1:1 ratio to receive either EDP 235 [REDACTED], EDP 235 [REDACTED], or placebo orally once daily for 5 days. Randomization will be stratified by age (≤ 50 years or 51 to 64 years) and by the duration of COVID-19 symptoms (≤ 3 days or >3 days and ≤ 5 days).

The study includes 4 periods:

- Screening period will occur from Day -1 to Day 1. Screening should be completed as soon as possible, and the subject will be randomized within 24 hours of signing the ICF. A subject will be considered enrolled at the time of randomization.
- Treatment period will begin with the first dose of study treatment on Day 1 and will conclude with the end-of-treatment (EOT) visit on Day 5.
- Follow-up period will begin following the last dose of study treatment and will conclude at the end of follow-up (EOFU) visit on Day 33 (28 days after the last dose of study treatment).
- Long-term follow-up period (LTFU) will begin at Day 34 and concludes at the end-of-study (EOS) visit at Week 24.

An overview of the study design is shown in **Figure 1**. Study site visits and assessments are detailed in the Schedule of Study Procedures ([Appendix 14.1](#)).

Figure 1: Study Design

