2.4. Dose Adjustment/Modifications

Dose modifications are not permitted for subjects in this study.

3. General Statistical Considerations

Continuous variables will be summarized using n, mean, standard deviation, median, 25th percentile (Q1), 75th percentile (Q3), minimum, and maximum values. The precision for continuous variables will be based on the precision of the data itself. The mean, median, 25th percentile, and 75th percentile will be presented to one more significant figure than the original results; the SD will be presented to two more significant figures than the original results; the minimum and maximum will be presented to the same level of precision as the original results.

Categorical variables will be summarized using frequency counts and percentages. Percentages will be presented to 1 decimal place. If the count is 0, the percentage will not be displayed. If the count equals the denominator, the percentage will be displayed as 100.

When **count data** are presented, the percentage will be suppressed when the count is zero to draw attention to the non-zero counts. A row denoted “Missing” will be included in count tabulations as needed to account for dropouts and missing values. The denominator for all percentages will be the number of subjects in the treatment group within the analysis set of interest, unless otherwise specified.

Baseline, unless otherwise specified, will be defined as the last non-missing measurement collected prior to dosing on the same date as the first dose of study treatment; if it is not available, the first measurement up to 2 hours post first dose of study treatment will be used. For

subjects who are randomized, but not treated, the baseline will be defined as the last non-missing measurement on or before the date of randomization. For height, weight and body mass index baseline will be defined as the last non-missing measurement collected on or before the date of the first dose of study treatment (without consideration of time). .

Study Day 1 is the calendar day that the first dose of the study treatment is administered. Subsequent study days are calculated as the date of assessment/event – date of the first dose + 1. If a subject is not treated, the date of randomization is used to define study day rather than the date of first dose. For assessments or events that occur before the first dose date, study day is calculated as the date of interest minus the first dose date.

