7.1.2. Incidence of Adverse Events

An overview of TEAEs will be presented overall and by treatment, including the number and percentage of subjects with any:

- TEAEs
- Related TEAEs
- Grade 3 or higher TEAEs
- Maximum severity TEAE (Mild, Moderate, Severe, Life-Threatening, Death)
- TEAEs leading to study treatment discontinuation
- TEAE's leading to study discontinuation
- TEAEs leading to death
- Treatment emergent SAEs
- Related treatment emergent SAEs

All TEAEs will also be presented in a summary table by SOC and PT through end of study participation. A subject may have more than 1 TEAE for an SOC or PT. A subject with 2 or more TEAEs within the same level of summarization will be counted only once in that level. The summary of TEAEs will be presented in descending order from the SOC with the highest total incidence to the SOC to the lowest total incidence. If the total incidence for any 2 or more SOCs are equal, the SOCs will be presented in alphabetical order. The PTs within each SOC will be presented in alphabetical order.

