14.1.1. Schedule of Study Procedures

| Period | SCR | Treatment | | | | Follow-up ^a | | | | | | LT Follow-up | | Notes | | |
|----------------------------|----------------------|----------------|----|------------------|----|------------------------|------------------|------------------|------------------|------------------|------------------|------------------|------------------|------------------|-------|--------------------------------------------------------------------------------------------------------------------------------------------------------------------------------------------------------------------------------------------------------------------------------------------------------------------------------------------------------------------------------------------------------------------------------------------------------------------------------------------------------------------------------------------------------------------------------------------------------------|
| | | 1 ^c | 2 | 3 | 4 | 5 ^c | 6 to 8 | 9 | 10 to 13 | 14 | 15 to 32 | 33 | Wk 12 | | Wk 24 | |
| Day | -1 to 1 ^b | 1 ^c | 2 | 3 | 4 | 5 ^c | 6 to 8 | 9 | 10 to 13 | 14 | 15 to 32 | 33 | Wk 12 | Wk 24 | | |
| Visit Name | SCR | V1 | T1 | V2 | T2 | EOT | V3 | V4 | V5 | V6 | EOFU | V7 | V8 | EOS | | |
| Type of Visit | C | C | T | C/H ^f | T | C/H ^f | C/H ^f | C/H ^f | C/H ^f | C/H ^f | C/H ^f | C/H ^f | C/H ^f | C/H ^f | | |
| Eligibility | | | | | | | | | | | | | | | | |
| Informed consent form | X | | | | | | | | | | | | X* | | | Informed consent must be obtained before conducting any study specific assessments. *Participants who completed the study at the EOFU (Day 33) visit will be asked to participate in the long-term follow-up. If the participant agrees to participate, informed consent must be obtained for the long-term follow-up. Protocol Section 12.1.3 AEs, concomitant medications and therapies, and medically attended visits should be captured in the eCRF retrospectively for subjects who re-enter the study; data will be collected starting the next day after the participant completes the EOFU visit. |
| Inclusion/exclusion review | X | X | | | | | | | | | | | | | | Protocol Section 4.1 and Protocol Section 4.2 |

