14.5. Imputation Rules

Imputation rules for missing or partial AE start/end dates and times are defined as:

- If Time (start or end) of any AE is missing and corresponding date is also not missing, then impute as 23:59.
- Only Day of AE start date is missing:
 - If the AE start year and month are the same as that for the first dose date, then:
 - If the full (or partial) AE end date is NOT before the first dose date or AE end date is missing, then impute the AE start day as the day of first dose date.
 - Otherwise, impute the AE start day as the first day of the month.
- If Day and Month of AE start date are missing:
 - If AE start year = first dose year, then:
 - If the full (or partial) AE end date is NOT before the first dose date or AE end date is missing, then impute the AE start Month and Day as the Month and Day of first dose date.
 - Otherwise, impute the AE start MONTH as January and the DAY as 1.
- If Year of AE start date is missing:
 - If the year of AE start is missing or AE start date is completely missing, then query site and leave as missing.
- For missing and partial adverse event end dates, imputation will be performed as follows:
 - If only the day of the month is missing, the last day of the month will be used to replace the missing day.
 - If the day and month are missing or a date is completely missing, it will be considered as missing.

Imputation rules for missing or partial medication/therapy start/stop dates are defined below:

- If only Day of start date is missing:
 - If the start year and month are the same as that for the first dose date, then:
 - If the full (or partial) end date is NOT before the first dose date or end date is missing, then impute the start day as the day of first dose date.
 - Otherwise, impute the start day as 1.
- If Day and Month of start date are missing:
 - If start year = first dose year, then:
 - If the full (or partial) end date is NOT before the first dose date or end date is missing, then impute the start Month and Day as the Month and Day of first dose date.
 - Otherwise, impute the start MONTH as January and the DAY as 1.

- If Year of start date is missing:
 - If the year of start is missing or start date is completely missing, then query site and leave as missing.
- For missing and partial end dates, imputation will be performed as follows:
 - If only the day of the month is missing, the last day of the month will be used to replace the missing day.

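### AE start-date imputation in Appendix 14.5 ignores long-term follow-up, so partially dated long-term AEs can be counted as treatment-emergent; the Day 33/34 boundary also needs one consistent definition

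*SAP*

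**What the plan says.** - **TEAE window.** In SAP Section 7.1.1, AEs that start or worsen from the "first dose of study treatment through Day 33 are considered Treatment-Emergent Adverse Events (TEAEs"). This matches the primary endpoint in Table 1 (Section 2.2), which also runs through Day 33.
- **EOFU visit.** Section 2.1 places it on "Day 33 (28 days after the last dose of study treatment"). Section 4.1 allows a window: "last planned study visit (Day 33 ± 1 day"). After early treatment stop, footnote e of the Schedule of Study Procedures (14.1.1) sets it 28 days after the last dose taken.
- **Start of long-term follow-up.** Section 2.1 says Day 34. The consent note in 14.1.1 says "data will be collected starting the next day after the participant completes the EOFU visit", with capture retrospective for subjects who re-enter.
- **Long-term AEs.** Section 7.1 plans a separate summary on the SAF LTFU population, which contains only consenters (Section 3.4.7), and counts every reinfection as an AE. Footnote i of 14.1.1 has staff record COVID-19 signs and symptoms as AEs at Weeks 12 and 24.
- **Partial AE start dates.** In Appendix 14.5, if day and month are missing and the year is the first-dose year, the rule is to "impute the AE start Month and Day as the Month and Day of first dose date"; in another year it is 1 January. If only the day is missing, the date becomes the first-dose date when the month and year match, and otherwise the first of the month.
- **TEAE table horizon.** Section 7.1.2: "All TEAEs will also be presented in a summary table by SOC and PT through end of study participation".

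**The concern.** Imputing an ambiguous onset towards the treatment period is a sound convention when nobody knows on which side of the boundary the event began. An AE recorded under long-term follow-up is different: by the 14.1.1 note it began after the EOFU visit. Appendix 14.5 does not use that knowledge. It can assign a date that the subject's own record contradicts and then let that date decide TEAE status. AEs through Day 33 are the primary endpoint, so a reinfection reported at Week 24 with only a year could be tabulated as a Day 1 TEAE. Recall over weeks, with retrospective capture, is where partial dates are plausible.

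A second, smaller problem is that the period boundary is stated in more than one way, so two programmers could assign a Day 34 onset differently.

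**Working it through.** **Study-day arithmetic.** Section 3 gives the formula: "Subsequent study days are calculated as the date of assessment/event – date of the first dose + 1". The last planned dose is on Day 5, and 5 + 28 = 33, which reproduces the plan's Day 33. With ± 1 day, EOFU falls on Days 32 to 34. After a last dose on Day 1 to 4 it falls nominally on Day 29 to 32 (1 + 28 to 4 + 28).

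**Day and month missing.** The end date of a long-term AE cannot precede first dose, so that condition in 14.5 is always met.
- First dose 1 June, true onset 1 September (Day 93): same year, imputed to 1 June, Day 1.
- First dose 10 December, true onset 1 March (Day 82): next year, imputed to 1 January, Day 23.

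Both become TEAEs.

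**Only the day missing.** A Day 34 or later onset is at least 33 days after first dose, so it can never share the first-dose month. The date is therefore always the first of the onset month and never Day 1. It is a TEAE date only if that first of the month is Day 33 or earlier. The month ends at most 30 days later, so the latest true onset that can be drawn in is Day 33 + 30 = Day 63.
- First dose 20 September, true onset 28 October (Day 39): imputed to 1 October, Day 12, a TEAE.
- First dose 1 June, true onset 1 September: stays at Day 93.

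**Enumeration.** Assumptions: first-dose dates uniform over 365 days, true onsets uniform over Days 34 to 168 (135 days), so 365 × 135 = 49,275 combinations.

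| Missing part | Imputed to Day 33 or earlier | Exactly Day 1 |
|---|---|---|
| Day only | 5,373 / 49,275 = 10.9% | 0 |
| Day and month | 40,095 / 49,275 = 81.4% | 35,775 / 49,275 = 72.6% |

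The second row depends strongly on the calendar: 100% for first doses in January to June and in December, but 13% in November. Extending onsets to Day 169 gives 10.8%, 81.2% and 72.5%. All these shares are conditional on the date being partial. A fully dated AE is not moved, and one with the year missing is queried and left missing.

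**Day 34 boundary.** Take an EOFU visit on Day 34, within window, and an AE with onset that day.
- Section 7.1.1: not a TEAE, since 34 > 33.
- 14.1.1 note: long-term data start on Day 35, so the AE precedes them.
- Section 2.1: long-term follow-up starts on Day 34, so the AE is long-term, but the SAF LTFU tables include it only if the subject consented.

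So the event can fall in neither period's SOC/PT tables: for everyone under the 14.1.1 start, and for non-consenters under either start.

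**The case against.** The strongest reply is that a fixed Day 33 cut is legitimate and matches Table 1, and that imputing towards treatment-emergent is conservative. The first half stands: the Day 33 cut should be kept. The second does not answer the point, because the onset of a long-term AE is not ambiguous with respect to EOFU.

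A reader might infer more than the SAP supports:
- **That Day 34 events vanish.** They do not. All AEs are listed (Section 7.1), and Sections 7.1.8 and 7.1.9 analyse the proportions with AEs and SAEs through Week 24.
- **That every EOFU visit held on Day 34 loses events.** TEAE status follows onset or worsening, not detection. An AE found on Day 34 that began by Day 33 is still a TEAE; only onset or worsening on Day 34 itself is affected.
- **That long-term AEs generally move to Day 1.** This needs both day and month missing and onset in the first-dose year.
- **That such AEs leave the long-term summary.** Section 7.1 does not say whether that summary uses imputed dates or excludes TEAEs.
- **That Section 7.1.2 extends the TEAE window.** Its table holds TEAEs, which 7.1.1 already limits to Day 33, and Section 4.1 treats the Day 33 visit as study completion. The phrase is loose and admits no later event.

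It is also fair that no count of affected AEs can be given, and that the 81% rests on assumed uniform enrolment.

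**Conclusion.** The imputation point holds. As written, Appendix 14.5 can turn an AE known to have started after EOFU into a TEAE. Under the uniform assumptions this happens to about 81% of long-term AEs missing day and month (13% to 100% by first-dose month; 73% on Day 1 itself) and about 11% of those missing only the day (none on Day 1, none with true onset after Day 63). These are shares of partially dated long-term AEs, not of all AEs. The SAP does not say how many there will be, and the number may be small. The rule should be changed because its result is wrong and correcting it is nearly free, not because a large effect on the primary tables has been shown.

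The boundary point is a drafting inconsistency limited to onset or worsening on Day 34. It affects the period SOC/PT tables, not the listing or the through-Week-24 proportions.

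**What to change.** 1. **Appendix 14.5.** For any AE collected in long-term follow-up with a partial start date, impute the latest of (a) the date given by the current rule, (b) the day after the EOFU visit and (c) Day 34. Imputation alone then cannot make the AE a TEAE. Part (c) is needed because the day after EOFU can itself be Day 33 or earlier, after a Day 32 visit or an early treatment stop. If the recorded month or end date itself places onset on or before Day 33, that recorded information should stand.
2. **Sections 2.1, 7.1 and 14.1.1.** Keep the Day 33 TEAE cut that matches Table 1. State one start for the later period, assign every AE with onset after Day 33 to the post-Day-33 summary, and say how that summary handles a Day 34 onset in a subject who did not consent to long-term follow-up.
3. **Section 7.1.2.** Delete the closing phrase on end of study participation.

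Cost: a few sentences in the SAP and a small programming change, with no new data. It should be settled before unblinding.
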